Based on prior studies,¹³ we expect a >25% within-trial decrease in postprandial blood glucose by WWB in high-responders compared to WB. While a statistically significant between-treatment effect is also expected, our study is designed to define ‘high-responders’ vs ‘low-responders’ towards precision nutrition rather than achieve group mean differences by bread treatment.¹⁴ In addition, we expect reduced serum endotoxin during WWB intervention, as metabolic endotoxemia is known to initiate insulin resistance in obese persons.^{41, 42} These benefits are expected to occur through an anti-inflammatory mechanism that attenuates gut-derived endotoxin translocation⁴³ or an antimicrobial activity of WWB that depletes pyrogenic Gram-negative bacteria. In support of the former, we expect WWB will decrease small intestinal and colonic permeability,⁴⁴ based on decreased urinary excretion of lactulose/mannitol and sucralose/erythritol. WWB may also alter, at least in a subset of the study participants, the gut microbial composition, as reported previously in both healthy adults as well as in persons with MetS (e.g. an increase of *Lachnospira*, *Faecalibacterium*, *Prausnitzii*, and *Prevotella copri* abundance and a decrease in *Enterobacteriaceae* abundance in the WWB group^{45, 46}). It is also possible to detect selective antimicrobial activities of WWB (possibly due to its rich phytochemicals)^{16, 47} and consequentially decreased LPS-producing Gram-negative bacteria. If these findings are consistent in a subset group of study participants who have larger changes of glycemic response post WWB intervention, they will collectively suggest a mechanism, at least in part, that the multi-facet health benefit of WWB consumption is gut microbiome-dependent. Meanwhile, with our combined targeted and untargeted metabolomics approaches, we expect a group of known (e.g., energy metabolism metabolites and amino acids)^{48, 49}, and unknown metabolic features may change significantly in fecal and blood metabolome between WWB and WB intervention. Taken together, these studies will establish a solid foundation for determining health and metabolic effects on the human host based on the composition and microbial metabolic capability of gut microbes.

IV. Pitfalls and Alternatives

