We plan to conduct a 2x2 *randomized, controlled, crossover trial* in persons with prediabetes (n = 40; 1:1 M/F) to assess 2-wk consumption of white bread (WB) vs whole wheat bread (WWB) on cardiometabolic and gut microbiome parameters (Figure 1). Participants will be recruited from the Columbus, OH area,

consistent with earlier successful studies conducted by the [name] lab. Participants will be block-randomized in 4-unit blocks to receive WB or WWB (128 g/day; 4 bread slices/d, according to the USDA “My Plate” recommendation and other similar studies)^{14, 53, 54} for 2-wks. During each study arm, participants will be provided standardized test meals containing WB or WWB, these foods will be prepared and packaged in the Human Nutrition Metabolic Research Kitchen (Evans Laboratory) to be devoid of whole grain products, probiotic-containing foods (e.g., yogurt), or fermented foods that are known to alter gut bacteria populations. Before and after each 2-wk study arm, a fasting blood sample will be obtained for metabolomic and clinical measures. Blood pressure and anthropometrics also will be assessed on days 1, 7, 14, and participants will collect a fecal sample to provide to the study team during their visits on day 1 and day 14. Lastly, on day 14, participants will simultaneously complete an oral glucose tolerance test and gut permeability test, which involves ingesting a glucose solution that also contains non-digestible sugar probes prior to collecting complete 24-hour urine samples for assessments of upper and lower gut permeability (described below). Upon completing these procedures, participants will undergo >2-weeks wash-out before repeating the study identically, but with crossover to the alternate bread diet.

B. Study Subjects

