2. Recruitment. We will recruit participants through posted flyers, e-mail, electronic and newsprint advertisements (e.g. campus student and faculty/staff newspapers, local and regional newspapers; see attachment “*Advertisements*”), and word of mouth. The posted advertisements will instruct interested participants to call the study center ([name] Laboratory, Department of Human Sciences) or complete an online pre-screening survey to obtain further information. During the phone-in hours, a trained individual (i.e. project coordinator or graduate assistant) will be available to describe the study and determine preliminary qualification by conducting a scripted phone interview (e.g. do you take dietary supplements?, do you smoke?; see “*Phone Script*” attachment). The individual will record answers and assess whether the person calling is likely or not to be an acceptable study participant. If the caller and the interviewer agree that the caller should participate, the prospective participant will be invited to a screening meeting, where the study will be fully described, and the individual will be provided a consent form to complete prior to any involvement in the study procedures. Data collected during this phase will include participant’s age, health status, physical activity, and contact information (see “*Informed Consent*” attachment).

3. Power Calculation and Data Analysis. [name] (biostatistician; *co-PI and Dept of Biomedical Informatics*) performed a power analysis. To ensure that the order by which each participant completes each trial is randomized, a random sequence generator (<http://www.random.org/sequences/>) will be used to determine the order by which each participant will undergo the two trials. We will primarily compare the

within-subject changes (WWB endpoint vs. WB endpoint) between high-responders and low-responders. We anticipate to have 6-12 high-responders and 5-10 low-responders of the total 40 study participants to achieve 80% power to detect a 1.6-fold difference in the changes of postprandial glucose levels (AUC from 0 to 180 minutes) between high-responders and low-responders, at the expected coefficient of variation (CV) 0.5 at a significant level of 0.05.

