2. *Blood Chemistries.* Fasting plasma glucose and lipids (total cholesterol, HDL-C, triglyceride) will be measured by clinical assay (Pointe Scientific) at screening, day 1, and day 14. Fasting insulin will be measured by ELISA (ALPCO) at day 1 and day 14. Postprandial glucose (0-180 min at 30 min intervals) following an oral glucose tolerance test will also be measured on day 14. At the beginning and the end of each intervention arm, we will define the effects of WWB on inflammatory responses. We will assess intestinal inflammation by measuring fecal calprotectin and myeloperoxidase (i.e. indices of neutrophil inflammatory responses) by ELISA as we described.⁵² We will also measure systematic inflammatory responses in both fasting and postprandial serum by ELISA (CRP, IL-6 and -8, TNF α , MPO) and by RTPCR analysis of peripheral blood mononuclear cells (PMBCs; isolated at blood collection) to assess the expression of genes involved in TLR4/NF κ B signaling (TLR4, MyD88, p65, IL-6 and -8, TNF α , MPO, MCP-1).

3. *Endotoxin.* Serum endotoxin from the individual participant will be assessed on day 1 and day 14 using a high-sensitivity fluorometric assay (PyroGene rFC; Lonza) and endotoxin-free consumables as reported in our previous studies.⁵⁵ In our hands, inter- and intra-assay CV is 4.2-6.1%.

4. *Preparation of Whole Wheat Bread.* To ensure uniformity in WB and WWB test products throughout this controlled study, both types of breads to be used will be prepared by co-Investigator [name] (Department of Food Science and Technology) and provided to the [name] lab for clinical study. WWB and WB will be prepared in the [name] lab in the Parker Food Science and Technology Building as previously reported by Cong et al.,⁵⁶ using the modified AACC straight-dough bread-making method.⁵⁷ The formula, is 200 grams of flour, included 10.6 g yeast (active dry), 12.0 g sucrose, 3.0 g salt (NaCl), 6.0 g shortening, and 130.0 g of water. Ingredients will be mixed (KitchenAid, Benton Harbor, MI) until a sponge dough is formed, approximately 2.5 min. The dough will be placed into a 5-3/4" x 3-1/4" x

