Separate LC-MS/MS procedures that are established by our research team, based on our published report,⁸⁷ and will be used to evaluate a panel of ten C₂-C₆ straight chain SCFAs (i.e. butyrate, acetate, propionate) and branched-chain SCFAs (e.g. isobutyric acid, isovaleric acid). Straight chain SCFAs are predominantly from bacterial fermentation of fibers whereas branched-chain SCFAs are derived mainly from bacteria metabolism of branched-chain amino acids. The former is often depleted with gut dysbiosis whereas the latter is often increased. In brief, fecal SCFAs are derivatized with 3-nitrophenylhydrazine to increase their stability prior to injecting on the LC-MS/MS system operated in negative ESI mode for quantitative analysis.

D. Detailed Study Procedures

1. Overview of Study Procedures. Potential participants who call the study center in an anonymous manner for more information will be given a brief description about the study and asked a few questions to determine their eligibility (*see Phone Script* attachment). If they meet the eligible criteria, they will be invited to the study center for a screening meeting. Prospective participants will be provided the Informed Consent form via email for review prior to an in-person discussion at the study center. During the in-person meeting, the Informed Consent (*see Informed Consent* attachment) will be explained and a hardcopy provided for them to review. If he/she chooses to participate in the study, they will then be asked to provide written consent. After receiving informed consent, the participants' height, weight, and blood pressure will be measured. Additionally, a small fasting blood sample will be collected for blood chemistry analysis. If they are not fasted at least 10 hours, they will be asked to come back in the fasted state at a time of mutual convenience. These blood results in combination with anthropometric parameters will determine the participant's eligibility. Eligible participants who agree to proceed with the study will then complete two 2-week intervention periods in a randomized order, each followed by a 3-h postprandial trial where a glucose tolerance test will be administered (Figure 1). We estimate that completion of all study procedures will take ~6-8 weeks per participant. Each study procedure will be discussed in detail below:

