 - *Day 10:* Participant will visit the study center briefly to pick-up meals that will be consumed on Days 11-14. Participant will return all uneaten foods and containers to the study team to determine actual food consumption during the preceding period. A stool collection kit will also be provided.
 - *Day 14:* Participant will visit the study center in the fasting state. The participant will provide a fecal sample that was self-collected during the preceding 24-hours. A urine sample will be collected to assess compliance to test meals. Participant will also return all uneaten foods and containers to the study team to determine actual food consumption during the preceding period. Anthropometrics and blood pressure will be assessed. Blood will be collected (0 min) and then an oral glucose tolerance test (75 g) and gut permeability test as described.⁵⁹ will be completed simultaneously. After emptying their bladder, the participant will ingest a 75 g glucose solution containing non-digestible sugars. Blood samples will be collected at 30-min intervals for 3-hours. Participant will be provided urine collection containers to self-collect urine for the subsequent 24-hours. During this 24-hour period, participants will also be provided controlled meals and beverages.
 - *Day 15:* Participant will return to the study center to provide collected urine. All procedures for Trial 1 are deemed complete.
- **Wash-out Period.**

Trial 1 and Trial 2 will be separated by at least two-weeks for men. However, the washout period for women may be extended to enable testing during the same phase (\pm 3 days) of the menstrual cycle.

- **Trial 2 Procedures (2-week intervention to WWB or WB).**

All procedures for Trial 2 will be identical to those of Trial 1 with the exception that the participant will receive the alternative test meals. If the participant was assigned WWB in Trial 1, WB will be assigned in Trial 2. If WB was assigned in Trial 1, then WWB will be provided in Trial 2.

- **Study Completion**

On Day 16 of Trial 2, the participant's involvement in the entire study is completed. A check will be provided to the participant in accordance with the payment schedule (up to \$350) that is outlined in the consent form.

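### With one OGTT per bread per participant, the trial cannot tell how much of its high- and low-responder labels is individual response and how much is test-to-test variation

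*Combined protocol and SAP*

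**What the plan says.** The aim is in section III (Anticipated Results): the study is meant to define responder groups "towards precision nutrition rather than achieve group mean differences by bread treatment". The same paragraph adds that "we expect a >25% within-trial decrease in postprandial blood glucose by WWB in high-responders compared to WB".

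Section VI.B.3 (Power Calculation and Data Analysis) makes the primary comparison that of "within-subject changes (WWB endpoint vs. WB endpoint) between high-responders and low-responders". Its power statement rests on the expected group sizes: "We anticipate to have 6-12 high-responders and 5-10 low-responders of the total 40 study participants". The mixed model there has diet and time as fixed factors and participant as the random factor. Correlations among features that change in high-responders, and logistic and ROC models of biological response, follow from it.

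The data come from a 2x2 crossover "in persons with prediabetes (n = 40; 1:1 M/F"), section VI.A. Section VI.C.2 places the glucose AUC at one time per arm: postprandial glucose "following an oral glucose tolerance test will also be measured on day 14". Section VI.D.1 describes two intervention periods, "each followed by a 3-h postprandial trial where a glucose tolerance test will be administered". Section VI.D.3 closes the schedule: "All procedures for Trial 2 will be identical to those of Trial 1", apart from the switch of bread. There is no day-1 OGTT, no repeat OGTT and no third or fourth period.

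Section IV foresees that too few responders may be found on glycemic response alone, and would then bring in HOMA-IR, endotoxin and inflammatory markers. No section discusses whether a label would recur if the person were tested again.

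**The concern.** To say that one person responds and another does not, an analyst needs to know how far the same person's result moves when nothing has changed. With one test per bread that quantity is not observed. The seven samples within an OGTT trace one curve; they are not repeat tests.

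Two things are at stake. First, the microbiota, metabolite and ROC analyses look for correlates of responder status, so any chance component in that status weakens real associations. Second, an apparent benefiting subset would also be seen if everyone had the same true effect. Section III would read consistent findings in a subset with larger glycemic changes as suggesting a microbiome-dependent mechanism.

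This is separate from choosing the cut-off after seeing the data, and from testing groups on the variable that formed them. A cut-off fixed in advance still acts on one noisy difference per person.

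**Working it through.** **The plan's own figure.** Section VI.B.3 claims 80% power for a 1.6-fold difference at CV 0.5 and alpha 0.05. On the log scale the SD is sqrt(ln(1 + 0.5²)) = 0.472, and the standardised difference is ln(1.6)/0.472 = 0.995. Exact two-sided t power is then 31% for 6 against 5 and 60% for 12 against 10. On the raw scale, 0.6/0.5 = 1.2 with a normal approximation gives 80% for 12 against 10 but 51% for 6 against 5. The 80% is thus matched only at the top of the stated range. That is a separate matter, and nothing below depends on it. The CV of 0.5 is not identified as within-person, between-person or of the change, so I do not use it as test-to-test variation.

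**Structure (no assumed figures).** For participant i, write the log ratio of AUC on WWB to AUC on WB as

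d_i = mean effect + b_i + (e_i,WWB − e_i,WB),

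where b_i is the individual departure from the mean effect and the e terms are test-to-test error. Then Var(d_i) = Var(b) + 2·Var(e). Each participant gives one d_i, so the data estimate the sum and not its two parts. In the mixed model, a participant-by-diet term would have one observation per cell and no error degrees of freedom. The mean effect remains estimable.

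**How many could pass a cut-off by chance.** Assumptions: log-normal AUC; test-to-test CV w from 5% to 25%; a cut-off at a 25% fall; no individual differences (b_i = 0); a common true ratio R of 1.0 or 0.9.

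- SD of d = sqrt(2)·sqrt(ln(1 + w²))
- P(apparent fall above 25%) = Φ[(ln 0.75 − ln R)/SD]
- Expected count = 40·P

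At w = 15%: SD = 1.414 × 0.1492 = 0.211. With R = 1.0, z = −0.2877/0.211 = −1.364, P = 0.0863, count 3.5. With R = 0.9, z = −0.1823/0.211 = −0.864, P = 0.1937, count 7.7.

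| Assumed CV | Count of 40, no mean effect | Count of 40, uniform 10% fall |
|---|---|---|
| 5% | 0.0 | 0.2 |
| 10% | 0.8 | 3.9 |
| 15% | 3.5 | 7.7 |
| 20% | 6.1 | 10.3 |
| 25% | 8.2 | 12.0 |

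The planned 6 to 12 is reached from about 20% with no mean effect, and from about 15% with a uniform 10% fall.

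**If individual differences do exist.** Let the true SD of the log response be 0.15 to 0.30 (an assumption) with CV 10% to 25%. The share of Var(d) that is true is SD²/(SD² + SD of d²). It runs from 0.0225/(0.0225 + 0.1213) = 0.16 (SD 0.15, CV 25%) to 0.09/(0.09 + 0.0199) = 0.82 (SD 0.30, CV 10%). By simulation around a mean 10% fall with the same cut-off, 38% to 71% of those labelled high-responders would be so labelled again. The trial's data could not show where in this range it lies.

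**Cost of the two groups.** Comparing only the extremes leaves out 40 − (12 + 10) = 18 to 40 − (6 + 5) = 29 participants. For a true correlation of 0.4 between a feature and the observed difference, at a single two-sided 5% test, power is about 75% using all 40, against about 51% to 62% using the extreme groups (simulated, good to a point or so).

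**The case against.** The strongest reply is that the documents promise less than a stable individual trait. Nowhere do they say that response will be reproducible. Section II.D asks whether gut bacteria could explain benefit in some individuals, and section III speaks of suggesting a mechanism in part. That is a group-level association, which label noise weakens but does not make meaningless. This stands, although the stated aim of defining responders for precision nutrition invites the stronger reading.

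The size is also open to challenge. The 25% figure is what the sponsor expects to see in high-responders, not a rule for assigning the label. The CV, the uniform fall and the true SD are all assumed. The plan also takes steps that may reduce within-person variation: supplied and controlled diets with weight monitoring (VI.C.5), menstrual-phase matching (VI.D.3), standard fasting (VI.G) and alkylresorcinol compliance checks (VI.C.8). All of this is fair. These steps may reduce the noise, but none measures it.

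A reader might infer that the labels are mostly noise. The documents do not support that: at CV 10% the true share exceeds one half for each SD tried (0.53, 0.67 and 0.82 for 0.15, 0.20 and 0.30).

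Finally, a continuous difference carries the same single-pair noise as a label, and the mixed model is not stated to be confined to the extreme groups. Both are correct. The continuous analysis recovers information lost by grouping; it does not cure the confounding.

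**Conclusion.** The point holds in a limited form. It rests on the schedule alone that individual response and within-person error are confounded; no assumed figure is needed, and no section of the plan resolves it. What is established is that the trial cannot tell signal from noise in the label, not that noise dominates.

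The chance counts are an illustration conditional on the CV, the cut-off and the common effect shown. They do not mean that the expected 6 to 12 high-responders are a chance product: at a CV of about 5% almost nobody would cross a 25% cut-off by noise. Nor does it follow that the trial is uninformative, since the mean WWB-WB effect and group-level associations with the microbiota can still be estimated, the latter with some loss.

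Severity: should-fix. The stated purpose and the primary comparison are affected, but the remedy lies in the analysis and in what is claimed.

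**What to change.** In sections III and VI.B.3:

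1. Make the main microbe and metabolite association analyses use the continuous WWB-WB difference in AUC in all 40 participants. Keep the high- and low-responder groups as a descriptive display. Say that this recovers power but leaves the single-pair noise in place.
2. State that a label describes one observed pair of periods, and that the trial cannot show that a person is a reproducible responder, or that a benefiting subset exists, on the labels alone.

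The cost is wording and an analysis specification, with no new visits, samples or participants. The downside is a more modest precision-nutrition claim.

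Two other remedies do less. The two day-1 fasting samples could inform within-person variation in fasting glucose and HOMA-IR, but not in OGTT AUC. Reporting a chance count would need a cut-off and a CV that the plan does not have. Only repeat OGTTs on each bread would supply the missing error term; that means extra visits, and this point does not ask for it.

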Recruitment. We acknowledge the challenge to recruit adults with prediabetes for a nutrition study during this unusual time of pandemic. Consistent with our previous studies,⁵⁰⁻⁵² we will consult the recruitment office of the OSU CCTS for assistance. They maintain a participant database (>126K registrants) and provide marketing support for study recruitment (e.g. social media, printed flyers, e-newsletters reaching ~100K faculty/staff and students at OSU).

[figure not shown]
All proposed procedures are well-established and frequently utilized by our research team. We, therefore, do not expect potential technical problems. However, we acknowledge the challenge of the potential interpersonal variability of dietary responses to WWB among the enrolled study participants, and there may be difficulties to identify sufficient “high-responders” and “low-responders” based solely on the glycemic responses. If needed, we will combine other health parameters, such as HOMA-IR, serum endotoxin, and select inflammatory biomarkers, to define response indicators for their gut microbiome dependency.

V. Significance of the Research and Potential Benefits

Whole grain, especially whole wheat food, is a recognized, important part of healthy dietary patterns due to its high abundance of fibers, protein, and bioactive phytochemicals. However, from both clinical trials and observational studies, controversy persists to clearly define the advantage of having incorporating whole wheat into the diet to manage metabolic disorders including prediabetes. Gut microbial composition and their metabolism, as recently emerged in many exciting studies, may play a critical role in determining the health benefits of having whole wheat in a regular diet in diverse populations. Therefore, our study is **significant** because it will provide critical data to help resolve the controversy by studying the gut microbiome-mediated, personalized effects of whole wheat intake in persons with prediabetes. Specifically, the integration of our multi-omics workflow coupled with studies in humans and in vitro will advance an understanding of the metabolic signatures of gut bacteria function to control the risk of prediabetes/glucose intolerance

VI. Procedures

A. Overview of Study Design

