Mixed effect modeling will be performed, diet and time will be included as fixed factors while participant serves as a random factor. False discovery rate (FDR) will be used to control type I error rate for microbiome and metabolome data, while the Bonferroni method will be applied for other measures (e.g., inflammatory markers). Data will be first normalized before analysis. Spearman correlations will be calculated to define associations between microbes, inflammatory genes, metabolites that show significant changes in highresponders.

To test whether the changes in microbes after WWB intake associate with the biological response, logistic regression will be fitted to each of the potential microbes or as a combination. We will also couple the logistic regression with receiver-operating characteristic (ROC) analysis to evaluate the specificity and sensitivity of the microbes that predict participants' biological response, and the area under the curve (AUC) of the microbial model will be displayed. Data analysis will be performed in R (open resource) or SAS (SAS, Inc; Cary, NC). The sample size was calculated in PASS 20 (NCSS, LLC; Kaysville, Utah).

C. Measurement/Instrumentation

All procedures will take place in the Human Nutrition Program located in Evans Laboratory. Infrastructure that is present includes a metabolic research kitchen, a private office to meet with participants, a clinical research laboratory for performing phlebotomy and research procedures, and a separate biochemical laboratory for processing and preserving biological specimens.

1. *Anthropometric Parameters and Blood Pressure.* At screening, day 1, 7, and 14, participants will rest for 15 minutes prior to determining blood pressure using an automated blood pressure cuff. BMI will be calculated from height determined from a wall-mounted stadiometer and weight from a calibrated scale.

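### Responder status, the grouping in the primary comparison, may be redefined after glycaemic responses are seen, so type I error for the microbe-response link is uncontrolled

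*Combined protocol and SAP*

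**What the plan says.** Section VI.B.3 (Power Calculation and Data Analysis) states that the primary comparison is of "within-subject changes (WWB endpoint vs. WB endpoint) between high-responders and low-responders". It expects small groups: "We anticipate to have 6-12 high-responders and 5-10 low-responders of the total 40 study participants". These are said "to achieve 80% power to detect a 1.6-fold difference in the changes of postprandial glucose levels (AUC from 0 to 180 minutes").

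Response status also drives the later analyses in that section: "To test whether the changes in microbes after WWB intake associate with the biological response, logistic regression will be fitted", followed by ROC analysis. Spearman correlations are planned for features that change significantly in high-responders. Section II.D (Summary) describes the same contrast for gut microbiota composition.

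Section IV foresees difficulty in finding enough high- and low-responders from glycaemic response alone, and continues: "If needed, we will combine other health parameters, such as HOMA-IR, serum endotoxin, and select inflammatory biomarkers, to define response indicators". The sentence ends by giving the purpose: "to define response indicators for their gut microbiome dependency".

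The only number attached to responder status is a fall of more than 25% in postprandial glucose in high-responders (section III, Anticipated Results). It is an expected result, not a cut-off, and low-responders have no number at all.

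**The concern.** The clause is a written permission to change the grouping variable, not just a missing definition. Whether it is needed can be judged only after the glycaemic responses have been looked at. The replacement markers are given by example, and the inflammatory ones are left to be chosen. Section VI.C.2 (Blood Chemistries) offers five serum proteins, two faecal markers and a panel of expressed genes to choose from.

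Two things are at stake. The first is the error rate of the link between microbes and response, which is the trial's central question. The second is what that link would mean. Section III expects WWB to lower endotoxin, possibly by depleting LPS-producing Gram-negative bacteria. If endotoxin helps define response, a microbe-response association no longer shows a microbiota-mediated glycaemic benefit.

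**Working it through.** **1. The plan's own figure.** Inputs from section VI.B.3: ratio 1.6, groups of 6-12 and 5-10, and "at the expected coefficient of variation (CV) 0.5 at a significant level of 0.05". Sidedness is not stated; two-sided is taken here. Power ≈ Φ(d·√(n₁n₂/(n₁+n₂)) − 1.960).

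- Raw scale, d = 0.6/0.5 = 1.20. For 12 v 10: 1.20 × 2.335 = 2.80, power 80.0% (t-test 76.0%). For 6 v 5: 1.20 × 1.651 = 1.98, power 51% (t-test 42.5%).
- Log scale, d = ln 1.6/√ln(1 + 0.5²) = 0.470/0.472 = 0.995. For 12 v 10: power 64% (t-test 60%). For 6 v 5: 38% (t-test 31%).

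The stated 80% is reproduced only at the top of the range, on the raw scale, with the normal formula. Small responder groups are therefore a real problem for this plan, which makes use of the fallback plausible.

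**2. Error rate for one microbe unrelated to any marker.** Null simulation: 40 people, top and bottom groups taken on each definition (12 v 10, 10 v 8 or 6 v 5), t-test at 0.05. Correlation between markers is 0 to 0.6, which is an assumption because the documents give none.

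| Use of the clause | Type I error |
|---|---|
| One definition fixed in advance | about 5% |
| One switch, made only on responder count, one result reported | about 5% (4.2-6.1%) |
| Glucose-only and one composite, better result kept | 8-10% |
| Four indicators plus a composite, best kept | 17-22% |
| Eight indicators plus a composite, best kept | 26-37% |

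If the definitions were independent, 1 − 0.95^k would give 9.75% for k = 2, 22.6% for k = 5 and 37.0% for k = 9. The simulated values lie at or below these to within simulation error, as expected for correlated definitions.

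**3. Existing safeguards.** FDR (microbiome and metabolome) and Bonferroni (other measures), both in section VI.B.3, count measures, not responder definitions. Section VI.F (Internal Validity) keeps sample codes until analysis is verified. That limits measurement bias but does not fix the responder rule.

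**4. The glucose comparison.** Generate within-person AUC differences as pure noise in 40 people, group on those differences, then test the same differences between groups. The test rejects in 100% of runs, for 12 v 10 and for 6 v 5. Grouping on a composite of glucose with one to seven independent markers gives 99% falling to 51%. The comparison is circular before any fallback is used; the fallback reduces the rate but leaves it far above 5%.

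**5. What a continuous response would gain.** People left out of the high/low comparison: 40 − (12 + 10) = 18 up to 40 − (6 + 5) = 29. With all 40, the correlation detectable with 80% power is tanh[(1.960 + 0.842)/√37] = 0.43. Simulating extreme groups from 40 bivariate-normal pairs, 80% power needs a full-sample correlation of about 0.48 (12 v 10) or 0.54 (6 v 5).

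**The case against.** The strongest reply is that the contingency is disclosed in advance and its trigger is the number of responders, not a non-significant result. The text also speaks of combining parameters, which suggests one composite and not a search through markers. Used that way, the error rate for an unrelated microbe stays near 5%. This stands as a limit on the size of the problem. It does not remove the problem, because the plan sets no count that triggers the switch, no composite and no limit on attempts.

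A reader might infer that the clause inflates false positives several-fold. The documents do not support that. It would take about four or more definitions with the choice made on the result, and no section describes such a search.

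A reader might also call it outcome switching. Section IV confines the fallback to indicators for the microbiome question; it does not replace glucose AUC as the measured outcome.

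It is fair, too, that the 0.05 in section VI.B.3 belongs to the glucose power statement and that microbes are to be tested under FDR control. The rates above are therefore illustrations for a single test, not the error rate of the full microbe analysis. FDR control still assumes one responder definition.

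Finally, comparing extremes is a legitimate design that keeps much of the information. Treating the 22 or 11 people as a random subsample would put the detectable correlation at 0.57 or 0.76, which overstates the loss.

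**Conclusion.** The concern holds in a limited form. The grouping for the primary, microbiota, logistic and ROC analyses can be changed after glycaemic data are seen, nothing bounds the change, and no multiplicity rule covers it. Type I error for the microbe-response link is uncontrolled. It need not be large: about 5% for a count-driven switch, 8-10% for one result-driven redefinition, and about 20% or more only with five or more definitions and the best kept. These figures assume marker correlations of 0 to 0.6, a single microbe at 0.05, and all 40 participants completing.

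Two conclusions do not depend on those assumptions. A response defined partly by endotoxin or inflammation supports a different claim from a glycaemic one. And the glucose-AUC comparison between glycaemic responder groups is circular whichever way the clause is used, so it can only be descriptive.

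**What to change.** Remove the fallback from the primary analysis. Before any outcome data are examined, fix one response variable: the within-person WWB-WB difference, or log ratio, in glucose AUC from 0 to 180 minutes. Relate it as a continuous variable to microbiota and metabolites in all 40 participants, keeping the planned FDR control across features. This removes the sparse-group problem that motivates the fallback and lowers the detectable correlation from about 0.48-0.54 to about 0.43 for a single test.

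Present the glucose-AUC contrast between high- and low-responders as descriptive only. Report any high/low split at a cut-off stated in advance, and any composite with HOMA-IR, endotoxin or inflammatory markers, as labelled exploratory or sensitivity analyses.

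The cost is analysis-plan wording, plus losing the option to rescue a sparse responder group within the primary analysis.
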